6.0 Imaging and Treatment Plan

**Phase II,
Dosimetry-Guided, Peptide Receptor Radiotherapy (PRRT) with
⁹⁰Y-DOTA-tyr³-Octreotide (⁹⁰Y-DOTATOC) in Children and Adults
with Neuroendocrine and other Somatostatin Receptor Expressing Tumors**

Treatment Cycles and Followup		Imaging and Treatment Schedule	Initial ⁹⁰ Y-DOTATOC Dose	Cumulative ⁹⁰ Y-DOTATOC Dose	Cumulative Renal Radiation
Cycle 1 Week 1	Day 1	Physical exam with height, weight, vitals, labs, list, GFR, pregnancy test; QOL questionnaire Start 18 hrs IV/PO fluids			
	Day 2	⁹⁰ Y-DOTATOC + IV amino acids Continue IV/PO fluids for 48 hrs	50 mCi/m ² in children; 120 mCi in adults	120 mCi maximum	
	Day 4	⁹⁰ Y-DOTATOC PET/CT			
Cycle 2 Week 7-9	Day 1	Physical exam with height, weight, vitals, labs, med list, GFR, pregnancy test Start 18 hrs IV/PO fluids			
	Day 2	⁹⁰ Y-DOTATOC + IV amino acids Continue IV/PO fluids for 48 hrs	Dosimetry determined	270 mCi maximum	
	Day 4	⁹⁰ Y-DOTATOC PET/CT			
Cycle 3 Week 13-17	Day 1	Physical exam with height, weight, vitals, labs, list, GFR, pregnancy test Start 18 hrs IV/PO fluids			
	Days 2-3	⁹⁰ Y-DOTATOC + IV amino acids Continue IV/PO fluids for 48 hrs	Dosimetry determined	420 mCi maximum	≤ 23 Gy
FU	3 months after treatment 3	Physical exam with height, weight, vitals, labs, med list, GFR; QOL questionnaire, diagnostic CT (MRI)			
	6-9 months after treatment 3	Physical exam with height, weight, vitals, labs, med list, GFR; diagnostic CT (MRI) ⁶⁸ Ga-DOTATOC PET/CT;			

Treatment consists of 3 cycles, 6-8 weeks apart. Cycle 1 dose is fixed. Cycles 2 and 3 doses will be determined by dosimetry-based calculation of renal doses from previous cycles; total renal dose ≤ 23Gy.

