6.3 Measurement of Renal Dose

The following information is required to estimate the dose to the kidneys:

- a) An estimate of the radioactivity accumulated in the kidneys,
- b) The kinetics of the radioactivity, and
- c) The size (mass) of the kidneys.

The renal accumulation of the radiopharmaceutical will be measured with Y-90 DOTATOC time-of-flight PET-CT imaging. A standard of Y-90 will be also imaged. PET images will be reconstructed with an OSEM iterative algorithm that incorporates the time of flight information. The kidney mass will be obtained from CT images.

The methods of kinetic analysis of the renal clearance of Y-90 DOTATOC is modified based on our previous experience. Our analysis of 47 prior administrations demonstrate that the renal clearance of Y-90 DOTATOC follows a biexponential pattern with the majority of the radiation exposure to the kidneys coming from the slow (long) component of clearance after the initial fast elimination. The rate constant of the slow component was gaussian distributed with a standard deviation less than 30% of the mean. This allows us to use a population based rate constant for slow clearance adjusted based on the uptake at 48 hours. The estimated renal radiation dose using this approach shows excellent correlation with the measured radiation dose (See *Appendix 1t: Single Timepoint Dose Estimate for Exponential Clearance*) and allows for a clinically feasible personalized treatment dosimetry with one follow-up visit after 48 hours of treatment administration. The information on renal uptake, renal mass and residence time will be entered into OLINDA software to calculate the radiation dose.

The Phase II studies of ⁹⁰Y-DOTA-tyr³-Octreotide administered to adults suggest that the safe range of ≤ 23 Gy for radiation to kidneys delivered by external beam radiation, is more likely 30-35 Gy when delivered as divided doses of targeted internal radiation⁵⁸. Furthermore, there were no dose limiting renal toxicity events in children or young adults enrolled in the Phase I study. Nevertheless, because of the young age of pediatric subjects described in Aim 1, we limited the total dose to kidneys, including any previous external beam radiation to ≤ 23 Gy. The dose to kidneys measured in Cycles 1 and 2 will be summated for each subject. If this total dose is < 23 Gy, the remaining allowable body activity for that subject will be calculated according to the following formula:

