10.0 Dosing Delays/Dose Modifications

10.1 Dosage Modifications

Dosimetry will be acquired following treatments 1 & 2. The kidney dose/mCi will be calculated and the total target dose that will limit renal dose to ≤ 23 Gy. The target dose minus 120 mCi will then be divided into two equal doses for Cycles 2 and 3 with adjustments based on dosimetry. Regardless of the total dose to kidneys as determined by dosimetry, the maximum dose in Cycle 2 will be 150 mCi; Cycle 3 will be limited to \leq Cycle 2.

Dose of ^{90}Y -DOTATOC will be decreased 25-50% for any subject in whom dosimetry measurement on first or second dose indicates probable total renal dose for three cycles will be >23 Gy. Dose may be increased on subsequent cycles so long as summation of dosimetry measurements limits total renal dose to ≤ 23 Gy.

Dose of ^{90}Y -DOTATOC will be increased 10-20% for any subject in whom dosimetry measurement on first or second dose indicates probable total renal dose for three cycles will be significantly <23 Gy. No subject will receive > 420 mCi total dose of ^{90}Y -DOTATOC.

Subjects who had a nuclear GFR measured at baseline will be followed for nephrotoxicity by nuclear GFR. If they demonstrate a $\geq 30\%$ decrease in GFR as determined by nuclear GFR scan, their dose will be reduced by 50% on the next cycle. Full dose may then be given when GFR returns to 90% of baseline. Patients who experience $\geq 30\%$ decrease in GFR will be placed on an age appropriate dose of captopril or other ACE inhibitor.

Also, patients that experience a rise in serum creatinine above 1.2 (who previously had normal levels) will be hydrated and have their serum creatinine repeated. If the creatinine level after hydration remains

elevated above 1.2, then nuclear GFR will be measured. If applicable, dose reductions will be implemented as described above.

Nephrotoxicity as demonstrated by $\geq 50\%$ decrease in nuclear scan GFR will be considered a DLT if the resulting GFR is below normal for subject's age, height and weight. Subjects who experience a DLT are eligible to receive subsequent cycles of ^{90}Y -DOTA-tyr³-Octreotide at a reduced dose if the DLT has returned to baseline value within 9 weeks of the intolerated ^{90}Y -DOTA-tyr³-Octreotide dose. The subject's subsequent dose must be reduced to 50% of the intolerated dose.

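### Two dosing rules fail for small subjects: the 1600 mL amino acid minimum cannot be met in 4 h below 48.2 kg, and the Cycle 2/3 split deducts the adult 120 mCi from children

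*Combined protocol and SAP*

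**What the plan says.** All places are in the combined protocol and SAP.

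**Amino acids.** Section 6.3 gives the infusion to all subjects as a renal protectant. The rate may not exceed 8.3 mL/kg/h (450 mL/h at most) for 4 h, the starting rate is 300 mL/h or less, and at least 1600 mL must be infused. No weight exception is given. Section 6.1 mentions a longer infusion only where the rate has been cut for nausea. Section 13.5 repeats the rate but states no minimum volume. Section 5.1 admits subjects from 6 months of age.

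**Activity.** The schedule in Section 6.0 sets Cycle 1 at 50 mCi/m² "in children; 120 mCi in adults", and adds that "Cycles 2 and 3 doses will be determined by dosimetry-based calculation of renal doses from previous cycles". Section 10.1 defines a target activity that holds the renal dose to 23 Gy, and then: "The target dose minus 120 mCi will then be divided into two equal doses for Cycles 2 and 3 with adjustments based on dosimetry". It also states that:

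- "the maximum dose in Cycle 2 will be 150 mCi; Cycle 3 will be limited to" Cycle 2 or less, and no subject may exceed 420 mCi in total;
- dose "will be decreased 25-50% for any subject in whom dosimetry measurement on first or second dose indicates probable total renal dose" above 23 Gy;
- dose "will be increased 10-20% for any subject in whom dosimetry measurement on first or second dose indicates probable total renal dose" significantly below 23 Gy;
- "Dose may be increased on subsequent cycles so long as summation of dosimetry measurements limits total renal dose to" 23 Gy or less.

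After Cycles 1 and 2, if the summed renal dose is under 23 Gy, Section 6.3 says "the remaining allowable body activity for that subject will be calculated according to the following formula".

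**The concern.** Each rule is written around an adult and applied to everyone.

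For a light subject the infusion limits contradict each other. The site must break the minimum, the rate or the duration, and is not told which. This is the kidney-protecting measure in a trial whose main organ at risk is the kidney.

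Deducting 120 mCi is right only for someone who received 120 mCi. A child is charged for activity never given, so the plan stops short of the renal-limited target. That works against the stated aims of maximizing tumor dose within 23 Gy (Sections 3.1 and 4.1) and of optimizing it for every patient (Section 13.3).

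**Working it through.** **Plan's own figures.** Adult maxima are 120, 120 + 150 = 270 and 270 + 150 = 420 mCi. These match the schedule, so the 120 mCi in the split is the adult Cycle 1 activity.

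**Infusion volume** (inputs from Section 6.3)

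- Full rate for 4 h: 4 × 8.3 = 33.2 mL/kg, so the threshold is 1600 / 33.2 = 48.2 kg.
- First half hour at 300 mL/h: 150 + 3.5 × 8.3 × w = 1600, so w = 1450 / 29.05 = 49.9 kg.
- Volume in 4 h at the maximum rate: 332 mL at 10 kg, 996 mL at 30 kg, 1494 mL at 45 kg.

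An adult below the threshold is affected too.

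**Gap left by the split.** Let T be the target and C1 = 50 × BSA. With Cycles 2 and 3 each at (T − 120)/2, the planned total is C1 + T − 120. The gap to T is 120 − 50 × BSA for T from 120 to 420 mCi.

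| BSA (m²) | C1 (mCi) | Gap (mCi) |
|---|---|---|
| 0.5 | 25 | 95 |
| 1.0 | 50 | 70 |
| 1.5 | 75 | 45 |
| 2.0 | 100 | 20 |
| 2.4 | 120 | 0 |

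For T below 120 mCi the split is negative.

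**How much of the gap the subtraction causes.** With the activity actually given, Cycle 2 = min(150, (T − C1)/2). This reaches T only if T ≤ 50 × BSA + 300. At 1.0 m² and T = 400, the stated split gives 50 + 140 + 140 = 330 mCi and the corrected one 50 + 150 + 150 = 350 mCi. Only 20 of the 70 mCi is then due to the subtraction; the cap explains the other 50. At T = 420 both give 350 mCi.

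**Adding the 10–20% increase.** Kidney dose per mCi, d, is not in the documents, so the values below are assumptions. T = 23/d, with no earlier external-beam dose to the kidneys. The child is 1.0 m².

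| d (Gy/mCi) | T (mCi) | Cycle 2 by split (mCi) | Total, split alone | Total, split plus 10–20% | Corrected Cycle 2 (mCi) |
|---|---|---|---|---|---|
| 0.08 | 287.5 | 83.75 | 217.5 mCi, 17.4 Gy | 234.25–251 mCi, 18.7–20.1 Gy | 118.75 |
| 0.10 | 230 | 55 | 160 mCi, 16.0 Gy | 171–182 mCi, 17.1–18.2 Gy | 90 |

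The corrected plan reaches 23.0 Gy in both rows. With the increase, 2.9–5.9 Gy stays unused. At 1.8 m² and T = 300 the split gives 90 + 90 + 90 = 270 mCi; a 20% increase would give 90 + 108 + 108 = 306 mCi, so the whole gap can be closed.

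**Catch-up in Cycle 3.** At d = 0.08 the Section 6.3 formula would leave 287.5 − 50 − 83.75 = 153.75 mCi, but Cycle 3 may not exceed the 83.75 mCi of Cycle 2.

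**High kidney dose per mCi.** At d = 0.20, T = 115 mCi and the split is (115 − 120)/2 = −2.5 mCi. Three cycles of 50 mCi would project to 30 Gy, so the decrease rule can govern. A 50% cut gives 100 mCi, 20.0 Gy. A 25% cut, with Cycle 3 trimmed to the allowance, gives 50 + 37.5 + 27.5 = 115 mCi, 23.0 Gy.

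**If the bands instead start from the child's own 50 mCi**, totals are 12.8–13.6 Gy at d = 0.08 and 16.0–17.0 Gy at 0.10. Section 10.1 does not say which base applies.

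**The case against.** The strongest reply on dose is that Section 10.1 should be read whole. The split is subject to dosimetry adjustment, the 10–20% increase is worded as mandatory, and the 25–50% decrease deals with the cases where the split turns negative. This largely stands as to size. A reader might infer that children end treatment 95, 70 or 45 mCi short; the documents do not support that, because those are gaps before adjustment, and near the top of the range the 150 mCi cap would cause much of them under any rule. It does not rescue the rule itself: the general adjustment wording gives no amount, the increase leaves a 1.0 m² child short in both worked cases, and the Cycle 3 limit blocks later catch-up.

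A second reply is that whether a child should get more activity per cycle is a clinical judgment. That stands, and it is why the correction needs clinical confirmation. It is not a reason to deduct activity that was not given.

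On the infusion, Section 6.3 refers further dosing questions to the manufacturer's instructions. That does not remove a conflict between limits the protocol sets itself. A reader might infer that a 10 kg child is to be infused for 19.3 h (1600/83) to reach the minimum. No text directs that; the conflict is simply left unresolved.

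**Conclusion.** Both rules are wrong as written and should be fixed.

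The infusion conflict is the firmer point. It rests only on figures in Section 6.3 and affects every subject below 48.2 kg, or 49.9 kg with a 300 mL/h start.

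The split error is also certain in form: 120 − 50 × BSA mCi before adjustment for targets of 120–420 mCi, and wholly due to the subtraction only up to a target of 50 × BSA + 300 mCi. Its final effect is smaller and depends on assumed kidney dose per mCi and on how the percentage bands are read. A reader might infer a renal safety breach from the split. There is none: it errs toward under-dosing, and 23 Gy remains a ceiling. How often it matters is unknown, because the documents give neither the expected number of children nor their kidney dose per mCi.

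**What to change.** **Section 6.3.** Keep 1600 mL for subjects of about 50 kg or more (at 50 kg, 150 + 29.05 × 50 = 1602.5 mL). Below that, set a weight-based minimum no greater than the permitted rate delivers in 4 h. The upper bound is 33.2 mL/kg. Above 300/8.3 = 36.1 kg the 300 mL/h start lowers it, to 32.05 mL/kg at 50 kg, and a slower start lowers it further. The value needs clinical confirmation, since the documents give no pediatric amount. Section 13.5 contains no minimum to amend.

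**Section 10.1.** Replace 120 mCi with the Cycle 1 activity actually given, with the result not below 0. Keep the 150 mCi, Cycle 3 no greater than Cycle 2, 420 mCi and 23 Gy limits. State whether the percentage bands apply to the split or to the previous dose.

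**Cost.** An amendment to two rules, with no extra patients or visits. The downside is that planned activity per cycle rises for some children: at 1.0 m², from 55 to 90 mCi at 0.10 Gy/mCi and from 83.75 to 118.75 mCi at 0.08, against 50 mCi in Cycle 1. The clinical team should therefore decide whether a pediatric per-cycle ceiling is needed; the documents support no particular value.

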1.5 Study design

This is a Phase 2 peptide receptor radionuclide therapy trial of ^{90}Y -DOTATOC in patients with somatostatin receptor positive tumors. The somatostatin receptor targeting of the therapeutic will be checked with ^{68}Ga -DOTATOC PET-CT imaging prior to therapy. Treatment consists of 3 cycles, 6-8 weeks apart. Cycle 1 dose is fixed with Cycles 2 and 3 doses to be determined by dosimetry-based calculation of renal doses from previous cycles not to exceed 23 Gy for the total renal dose.

^{68}Ga -DOTATOC PET imaging and ^{90}Y -DOTATOC peptide receptor radionuclide therapy (PRRT) are readily available in Europe, but neither radiopharmaceutical is approved for use in the United States. We are presently conducting a safety and efficacy trial of ^{68}Ga -DOTATOC PET in adults and children under IND# 114,398, that to date has included over 220 subjects with no serious adverse events. We have conducted a single institution Phase I trial of ^{90}Y -DOTATOC therapy in children and young adults under IND# 61,907 with no serious adverse events¹³, and we have participated in a Phase II trial of ^{90}Y -DOTATOC PRRT in adults, also with no dose limiting toxicities²¹.

The total radiation dose to kidneys with PRRT using ^{90}Y -DOTATOC is currently limited to ≤ 23 Gy for both children and adults. Several reports, including dosimetry performed on children in our Phase I trial, have suggested that this dose limit can safely be raised to as high as 35 Gy to kidneys when performing individualized dosimetry measurements to guide therapeutic dosing of ^{90}Y -DOTATOC^{26,29,30}. We have considerable expertise in the development of theoretical models for dosimetry³¹, as well as experience in performing dosimetry in individual patients^{13,32}. These studies demonstrated a wide variation in renal dose, both between patients and between cycles in any given individual. In this Phase II therapeutic trial, we therefore propose to perform dosimetry for each patient during the first and second cycles of therapy. The method for performing the dosimetry will take advantage of a positron decay component of Yttrium-90 that will allow quantification of radiation dose using PET imaging to measure rate of ^{90}Y -DOTATOC into kidneys, coupled with semi-quantitative measurement of bremsstrahlung energy using single photon emission tomography (SPECT) to follow the body clearance of ^{90}Y -DOTATOC over 72 hrs after injection of the therapeutic dose.

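### Section 10.1 subtracts the adult 120 mCi from every child's target activity, and its percentage dose steps have no stated base or rank against the 23 Gy split

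*Combined protocol and SAP*

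**What the plan says.** Section 6.0 fixes Cycle 1 at 50 mCi/m² "in children; 120 mCi in adults", and adds that "Cycles 2 and 3 doses will be determined by dosimetry-based calculation of renal doses from previous cycles", with total renal dose at or below 23 Gy. Section 1.5 says the same: "doses to be determined by dosimetry-based calculation of renal doses from previous cycles not to exceed 23 Gy for the total renal dose".

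Section 10.1 turns this into dosing instructions.

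- **Split.** Kidney dose per mCi gives the total activity that stays within the 23 Gy limit. "The target dose minus 120 mCi will then be divided into two equal doses for Cycles 2 and 3 with adjustments based on dosimetry".
- **Caps.** Whatever the dosimetry shows, "the maximum dose in Cycle 2 will be 150 mCi; Cycle 3 will be limited to" no more than Cycle 2. No subject may exceed 420 mCi in total.
- **Percentage steps.** The dose "will be decreased 25-50% for any subject in whom dosimetry measurement on first or second dose indicates probable total renal dose" above 23 Gy over the three cycles. It rises by 10-20% if that projection is significantly below 23 Gy.
- **Later increase.** "Dose may be increased on subsequent cycles so long as summation of dosimetry measurements limits total renal dose to" 23 Gy or less.

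Section 6.3 adds a formula for the activity still allowable once the renal doses of Cycles 1 and 2 have been summed.

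**The concern.** The split subtracts the adult Cycle 1 dose from every subject's target, although Section 5.1 admits children from 6 months of age and their Cycle 1 activity depends on body surface area. A child who received less than 120 mCi is charged for activity never given.

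The percentage steps are mandatory in form, but Section 10.1 does not say what the percentage is taken of, what activity the three-cycle projection assumes, or whether the step or the split governs when they differ.

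Dosimetry-guided dosing is the intervention under test. Primary Objective 2 (Section 4.1) is to monitor toxicity while maximizing tumor dose within 23 Gy to the kidney. A rule that withholds activity the ceiling allows, or that two compliant investigators would apply differently, works against that objective and makes the tested regimen harder to reproduce.

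**Working it through.** **The plan's own figures.** 120; 120 + 150 = 270; 120 + 150 + 150 = 420 mCi. The cumulative maxima in Section 6.0 reproduce and are not in dispute.

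**Notation.** d is the renal dose from Cycle 1 in Gy. Gy/mCi is assumed constant across cycles unless stated. The documents give no distribution of d.

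**(a) Children.** Let the Cycle 1 activity be A₁ mCi.

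- Target activity = 23 × A₁/d.
- Literal split per cycle = (23A₁/d − 120)/2.
- Split with actual activity = (23A₁/d − A₁)/2.
- Shortfall = (120 − A₁)/2 mCi per cycle.

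Assume a child of 1.0 m² (A₁ = 50) with d = 8, so 0.16 Gy/mCi:

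- Target = 23/0.16 = 143.75 mCi.
- Literal: (143.75 − 120)/2 = 11.9 mCi per cycle; total 8 + 23.75 × 0.16 = 11.8 Gy.
- Actual: (143.75 − 50)/2 = 46.9 mCi per cycle; total 8 + 93.75 × 0.16 = 23 Gy.

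The shortfall formula needs both splits to lie between zero and the 150 mCi cap. For this child the target is 1150/d:

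- The actual-activity split reaches 150 mCi at d = 1150/350 = 3.29, and the literal split at d = 1150/420 = 2.74. At or below 2.74 Gy both give 150 mCi and there is no loss; between the two the loss is smaller.
- Above d = 1150/120 = 9.58 the literal split is negative. At d = 10 it is (115 − 120)/2 = −2.5 mCi, while the actual-activity split is (115 − 50)/2 = 32.5 mCi.

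**(b) Adults: split against percentage step.** Assume the base is 120 mCi for both later cycles and that the projection is three cycles of 120 mCi.

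- Trigger for the decrease: 3d > 23, so d > 7.67.
- Split per cycle = (2760/d − 120)/2 mCi.
- Percentage step = 60 to 90 mCi; totals if held for both cycles = 2d (50% cut) to 2.5d (25% cut).

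| d (Gy) | Projection (Gy) | Split (mCi) | Step (mCi) | Total with step (Gy) |
|---|---|---|---|---|
| 8 | 24 | 112.5 | 60-90 | 16-20 |
| 9.2 | 27.6 | 90 | 60-90 | 18.4-23 |
| 11.5 | 34.5 | 60 | 60-90 | 23-28.75 |
| 12 | 36 | 55 | 60-90 | 24-30 |

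- From 7.67 to 9.2 Gy even the smallest step cuts more than 23 Gy requires. At d = 8 the total activity is 240-300 mCi against 345 mCi, which is 30% to 13% less. Both answers meet the ceiling, so the ceiling cannot choose.
- The later-increase sentence cannot restore the loss: the only cycle left is Cycle 3, and it may not exceed Cycle 2.
- From 9.2 to 11.5 Gy the split lies inside the band, so the rules can agree.
- Above 11.5 Gy a 50% cut held for both cycles would pass 23 Gy, so the ceiling forces the split or less.

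**Increase step, same base.** The most a 20% step gives is 120 + 144 + 144 = 408 mCi. The 420 mCi maximum needs 150 mCi per later cycle, which is +25%.

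**Alternative base: percentages as adjustments to the split.** The split projects 23 Gy or less by construction, so a decrease can never be triggered by first-dose dosimetry, although the text names the first dose. After the second dose it can be triggered if Gy/mCi rises, and Section 1.5 reports "a wide variation in renal dose, both between patients and between cycles in any given individual". An increase after the second dose would put Cycle 3 above Cycle 2, which the cap forbids.

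**The case against.** The best defence is that 23 Gy is an upper limit and not a dose to be reached. A patient who gets 60-90 mCi per cycle at d = 8 is within it, and a protocol that writes 25-50% has chosen to leave room for judgement. This stands in part: the lower dose breaches no limit. But Section 10.1 also says what the split is, the step gives a different activity for the same measurement, and no text says which to use. The discretion lies inside the band; at d = 8 the split lies outside it.

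A reader might infer that the percentage rule allows renal doses above 23 Gy, since Cycles 1 and 2 alone would pass it above d = 23/1.75 = 13.14 with a 25% cut, or above d = 23/1.5 = 15.33 with a 50% cut. The documents do not support that. Sections 1.5 and 6.0 apply the ceiling prospectively to Cycles 2 and 3, and Section 10.1 opens with the same limit. The Section 8.1 stop, which acts only once the limit is exceeded, is not the main control.

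A reader might also infer that the percentage step contradicts the Section 6.3 formula whenever the two give different Cycle 3 activities. That goes too far. The formula gives a maximum, so a deeper cut is compatible with it. If r is the ratio of Cycle 2 to Cycle 1 Gy/mCi and Cycle 3 uses the Cycle 2 value, the cut needed from an uncapped split is 2 − 2/r, so a 25% cut suffices up to a 14% rise and a 50% cut up to 33%. With the mean of the two cycles the limits are about 18% and 40%. Section 6.3 does not say which value to use.

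The pediatric subtraction may be shorthand for the Cycle 1 dose, and its error spares the kidney. It is still the written rule, and it misses the tumor-dose aim.

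**Conclusion.** Both defects hold, and both err toward less tumor activity than Primary Objective 2 seeks.

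The pediatric subtraction is wrong as written and needs no assumption about the percentage base. Its size depends on body surface area and d: at the assumed 1.0 m² and 8 Gy it removes 35 mCi per cycle (46.9 − 11.9). It has no effect where both versions reach the 150 mCi cap.

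The percentage steps are ambiguous on any base. The 7.67-9.2 Gy range and the 13-30% loss at 8 Gy rest on a 120 mCi base, a projection of three 120 mCi cycles and constant Gy/mCi.

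This is a matter of precedence and consistency. No stated maximum is wrong, the 23 Gy ceiling outranks both rules, and no effect on the efficacy decision rule or sample size is shown. The number of patients affected is unknown.

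**What to change.** Amend Section 10.1 to:

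1. Subtract the subject's actual Cycle 1 activity in place of 120 mCi.
2. State that the split sets Cycle 2 and that the Section 6.3 residual formula caps Cycle 3, subject to the 150 mCi, Cycle 3 ≤ Cycle 2 and 420 mCi limits.
3. Make the 25-50% and 10-20% steps subordinate to these rules with a stated base, or delete them if the clinical team agrees.
4. Reconcile the later-increase sentence with Cycle 3 ≤ Cycle 2.

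The cost is a wording amendment, with no extra procedures or patients. The clinical team should confirm which rule was meant to govern.

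### Section 10.1 raises the Cycle 2 dose on projected kidney dose with no blood-count condition, and Section 10 gives no ANC or platelet threshold for retreatment

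*Combined protocol and SAP*

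**What the plan says.** Section 10.1 has two routes to a higher dose, and both work from kidney dosimetry.

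- **Percentage clause.** The dose "will be increased 10-20% for any subject in whom dosimetry measurement on first or second dose indicates probable total renal dose for three cycles" is low. The trigger is "probable total renal dose for three cycles will be significantly <23 Gy", and no number is given for how far below 23 Gy is enough.
- **Target rule.** The kidney dose per mCi fixes a total activity that keeps renal dose within 23 Gy. Then "The target dose minus 120 mCi will then be divided into two equal doses for Cycles 2 and 3". The limit is that "the maximum dose in Cycle 2 will be 150 mCi; Cycle 3 will be limited to" the Cycle 2 dose, with 420 mCi overall.

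Toxicity-based changes in Section 10.1 are renal only. After a GFR fall of 30% or more on nuclear scan, "their dose will be reduced by 50% on the next cycle". After a DLT, which is defined only by GFR, the "subsequent dose must be reduced to 50% of the intolerated dose". Sections 10.2 (Dose Delay) and 10.3 (Concomitant Therapy) contain no count criterion.

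Elsewhere, the Section 7.0 calendar puts a CBC with differential on Day 1 of Cycles 2 and 3, and Section 6.2 collects blood dosimetry as a stand-in for marrow dose. No dosing rule uses either. Section 8.1 ends an individual's treatment for unacceptable events, with irreversible hematopoietic toxicity as an example, or on investigator judgment. Section 12.2 stops the trial at four subjects with an irreversible non-renal Grade 4 toxicity. ANC and platelet floors (1000/mm3 and 90,000/mm3) appear only in inclusion criterion 10 of Section 5.1 and its checklist copy in Appendix III.

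**The concern.** A subject can reach Cycle 2 Day 1 with a low measured kidney dose and counts that have not recovered from Cycle 1. The dosing text then points upward, because kidney dose is the only quantity it consults. The CBC result is available the day before infusion, but the protocol does not say what to do with it. Whether the dose rises, holds or waits depends on the investigator stepping in.

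Hematologic toxicity is part of Primary Objective 2. Section 9.2 lists anemia, low white cells and low platelets among the observed effects and describes them as dose-related. Without a stated threshold, two subjects with the same counts and the same dosimetry can be dosed differently. That is a safety gap for the individual, and it makes the toxicity table harder to interpret.

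**Working it through.** **The plan's own figure.** Cycle 1 in adults is 120 mCi, Cycle 2 is capped at 150, and Cycle 3 may not exceed Cycle 2. The running maxima are 120, 120 + 150 = 270 and 270 + 150 = 420 mCi. These match the cumulative limits in the Section 6.0 table and the 420 mCi limit in Section 10.1.

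**Percentage clause, adult at 120 mCi.**
- 120 × 1.10 = 132 mCi
- 120 × 1.20 = 144 mCi

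Both are below 150, so the Cycle 2 cap does not block the increase.

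**Target rule, adult.** Let d be the Cycle 1 kidney dose in Gy from 120 mCi. Assume no earlier external-beam kidney dose and the same kidney dose per mCi in later cycles.
- Total activity for 23 Gy: 23 × 120/d = 2760/d mCi
- Cycle 2: (2760/d − 120)/2 = 1380/d − 60 mCi, capped at 150
- Above 120 mCi when d < 1380/180 = 7.67 Gy
- At the cap when d ≤ 1380/210 = 6.57 Gy (three-cycle projection at 120 mCi per cycle: 3 × 6.57 = 19.7 Gy)

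| Cycle 1 kidney dose d (Gy) | 1380/d − 60 (mCi) | Cycle 2 after cap (mCi) |
|---|---|---|
| 4 | 285 | 150 |
| 7 | 137 | 137 |
| 9 | 93 | 93 |

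**Size of the increase**, with Cycle 3 set equal to Cycle 2 and compared with 3 × 120 = 360 mCi:

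| Cycle 2 (mCi) | Rise over 120 | Three-cycle total (mCi) | Total vs 360 |
|---|---|---|---|
| 132 | 10% | 120 + 2 × 132 = 384 | +6.7% |
| 144 | 20% | 120 + 2 × 144 = 408 | +13.3% |
| 150 | 25% | 120 + 2 × 150 = 420 | +16.7% |

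**Cycle 3.** The percentage clause can also be triggered by the second dose. Applied again it would give 132 × 1.10 = 145.2 or 144 × 1.20 = 172.8 mCi. Either exceeds the Cycle 2 dose and so breaks the Cycle 3 cap. An increase over the previous dose can therefore take effect only at Cycle 2 if the cap governs.

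**Marrow safeguards.**

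| Place | Acts on the individual's next dose? | Count threshold? |
|---|---|---|
| Section 10.1, GFR and DLT rules | Yes | No; renal only |
| Section 8.1, unacceptable event | Yes, by ending treatment | No; the example is irreversible toxicity |
| Section 8.1, investigator judgment | Yes | No |
| Section 9.1, laboratory adverse events | Indirectly, through adverse-event delays | No; a lab value counts only if judged clinically significant |
| Section 12.2 | No; trial-level | Grade 4 and irreversible, four subjects |
| Section 5.1, criterion 10 | Reads as entry only | Yes: 1000 and 90,000 |

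The only row with usable count floors is the one whose application to Cycles 2 and 3 is in doubt.

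**The case against.** The strongest reply is that the protocol already protects the marrow. Criterion 10 is timed to study drug administration without the word first, whereas calendar footnote 6 says first when it means first. The CBC is repeated at each cycle, so the floors could be read as applying every time. That reading is possible. Against it, criterion 10 sits among the inclusion criteria, Section 10 never refers to it, and two of its components (bilirubin and urinalysis) are drawn at baseline only. Section 8.1 does name hematopoietic toxicity and does allow the investigator to stop. This stands, but it gives no number, and its example is irreversible toxicity rather than slow recovery.

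Four stronger readings are tempting, and the documents do not support them.
- *Renal toxicity is ignored too.* It is not. The GFR and DLT reductions are in the same section as the increase, and only the hematologic condition is missing.
- *The increase is automatic.* The wording is directive, but the trigger word, significantly, is undefined. Section 8.1 says only that treatment may continue. The investigator has latitude.
- *Every adult with a Cycle 1 kidney dose below 7.67 Gy is escalated.* Section 6.3 counts earlier external-beam radiation toward the 23 Gy, in a sentence about pediatric subjects. Exclusion 4 admits some prior kidney exposure, which would lower the break-even.
- *Doses of 132 to 150 mCi cause cytopenia.* Section 9.2 ties these effects to higher doses but gives no figures, and it says most patients recovered. Section 1.5 reports no dose-limiting toxicity in the earlier adult Phase II trial.

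A reader might also see an unresolved conflict over Cycle 3, because "Dose may be increased on subsequent cycles so long as summation of dosimetry measurements limits total renal dose". The cap is worded as a limit that holds whatever the dosimetry shows, while this sentence is permissive, so the cap is the better reading. Saying so removes the doubt. Less clear is whether "Full dose may then be given when GFR returns to 90% of baseline" is also bounded by the cap, but that is a side issue.

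**Conclusion.** The point holds in a limited form. Section 10.1 directs dose increases on projected renal dose without a hematologic condition, and Section 10 has no ANC or platelet retreatment threshold, although the counts are already in hand. In an adult the dosimetry rules can give 12 to 30 mCi (10% to 25%) more than the dose that preceded low counts. The three-cycle total is then 384 to 420 mCi against 360.

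The percentages assume a 120 mCi first dose, Cycle 3 equal to Cycle 2 and, for the target rule, no prior kidney radiation and a stable kidney dose per mCi. How often a subject has both a low kidney dose and unrecovered counts cannot be worked out from the documents, so no expected harm is claimed. Investigator judgment may prevent most of it. This is a cheap improvement to a safety rule, not a flaw that undermines the trial. Confidence is moderate, because criterion 10 can be argued to apply before each dose.

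**What to change.** Amend Section 10.1 as follows.

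1. Allow any dosimetry-based increase over the previous dose, by the percentage clause or the target rule, only if Day 1 ANC is at least 1000/mm3, Day 1 platelets are at least 90,000/mm3, and no GFR or DLT reduction applies. The count floors are the protocol's own entry values, offered as a default that the sponsor may change.
2. If these conditions are not met, do not increase. Leave any delay or further reduction to the investigator within Section 10.2.
3. State that GFR and DLT reductions override dosimetry-based doses.
4. State that the Cycle 3 cap at the Cycle 2 dose governs over an increase triggered by second-dose dosimetry.

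Item 1 refers to whether a renal reduction applies, not to a GFR change. It can therefore be used for adults with baseline creatinine of 1.2 mg/dL or less, who need no baseline nuclear GFR.

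The cost is protocol wording. No new test is needed, because the CBC is drawn the day before dosing. The downside is that some subjects with low counts receive a smaller dose than the renal limit would allow.
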